Baseline characteristics will be summarized by group. Any imbalances between the treatment groups for any demographic or baseline characteristic will be assessed based on clinical relevance in reviewing the summaries. For any differences deemed clinically relevant to the efficacy comparisons, exploratory analyses that include the imbalanced factor as a categorized covariate will be performed.

To account for the effect of baseline low-dose aspirin use in the study population on the rate of recurrent VTE after an initial provoked event, we will perform a pre-specified stratified efficacy analysis of patients receiving low-dose apixaban or placebo with low-dose aspirin compared with patients just receiving low-dose apixaban or placebo. We will calculate stratum-specific risk ratios (RR). Comparing the “crude” (overall or unadjusted) and stratum-specific risk ratios will enable us to determine whether aspirin modifies the effect of low-dose apixaban and to what extent. If the stratum-specific risk ratio is similar to the crude risk ratio, then there is minimal impact of low-dose aspirin. However, if the stratum-specific risk ratio differs from the unadjusted estimate by 10% or more, then low-dose aspirin modifies the effect of low-dose apixaban. We will conduct a similar analysis for the safety outcome of major bleeding.

We will also pre-specify subgroup analyses focused on the safety and efficacy of major populations of interest, in particular, elderly patients (age \geq 65 years), women, and those with persistent provoking factors of immobility, obesity, heart failure, chronic lung disease, chronic kidney disease, hemodialysis, chronic inflammatory/autoimmune disorder, and atherosclerotic cardiovascular disease.

Means, medians, and frequency distributions will be calculated for continuous variables. Number and percentages will be reported for binary and categorical variables. Differences between subgroups of interest will be examined using the chi-square or Fisher's exact test for binary and categorical variables and t-test or Wilcoxon Rank Sum for continuous variables (if the subgroups are of sufficient size for statistical comparison).

Safety outcome analyses will be performed among patients who received one or more doses of a study drug (Safety Population). All p-values reported will be two-sided. A p-value < 0.05 will be considered significant. All analyses will be performed using SAS software.

Interim Analysis

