6.2 Cohort Definition

In this section, we define a main cohort and four confirmatory cohorts for the analysis of efficacy and safety (**Table**).

Main Cohort (ITT): we will use the intention-to-treat (ITT) cohort since it maintains the original randomization scheme ("as randomized")⁵.

Confirmatory Cohort (MITT): the modified intention-to-treat (MITT) cohort consisting of all randomized patients who took at least one dose of the assigned treatment and did not undergo post-randomization exclusion.

Confirmatory Cohort (PP-1): Additional analyses will include a per-protocol (PP) population for subjects who took 80% of the study drug (or placebo).

Confirmatory Cohort (PP-2): Additional analyses will include a per-protocol (PP) population for subjects who took 80% of the study drug (or placebo) with censoring for either ISTH major bleeding or clinically relevant nonmajor bleeding event.

Confirmatory Cohort (Safety Cohort): In this cohort, we will only consider bleeding events (major bleed or clinically relevant non-major bleed) that occurred within 96 hours of taking a dose of the study drug (or placebo). The follow-up duration will be considered until the occurrence of a bleeding event or 96 hours after taking the last dose of the study drug (or placebo), whichever comes first.

6.2.1 Table. Analysis cohorts.

Analysis Set	Definition	Primary Efficacy-12-month recurrent symptomatic VTE	Primary Safety-12-month ISTH major bleeding
ITT	All randomized	Number of events Proportion Cumulative incidence Hazard ratio 95% confidence interval P-value	Number of events Proportion Cumulative incidence Hazard ratio 95% confidence interval
mITT	All randomized who took at least one dose of assigned treatment (apixaban or placebo) and did not undergo post-randomization exclusion	Number of events Proportion Cumulative incidence Hazard ratio 95% confidence interval	Number of events Proportion Cumulative incidence Hazard ratio 95% confidence interval
Per protocol without censoring for bleeding events	Subjects who took 80% of assigned treatment doses (apixaban or placebo)	Number of events Proportion Cumulative incidence Hazard ratio 95% confidence interval	Number of events Proportion Cumulative incidence Hazard ratio 95% confidence interval

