6.3 Baseline Demographics and Clinical Comorbidities Description

Understanding the baseline demographics and clinical comorbidities of a cohort is crucial for interpreting study results and drawing conclusions about the generalizability of findings. In the HI-PRO trial, a table of descriptive statistics will be provided to summarize the baseline demographics of the intention-to-treat cohort. The table will include information on logical and categorical variables, such as age, sex, race, and comorbidities. The numbers and percentages will be provided for these variables, allowing for an assessment of the distribution and prevalence of different characteristics among the study population. In addition to logical and categorical variables, the table will also provide information on continuous variables, such as body mass index, hemoglobin level, and serum creatinine level. For these variables, the mean and standard deviation (SD) will be provided to summarize the central tendency and variability of the data.

According to the recent statistical reporting guideline from some experts⁶, we will not provide p-values for testing the differences in baseline characteristics of the two assigned groups. However, the balances should be checked to see the quality of randomization by inspecting the standardized difference. We will consider the ones with a standardized difference >0.1 as clinically different. For a certain category whose observations are smaller than five counts, we may consider regrouping the categories.

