6.4 Survival Analysis

6.4.1 Principal Analysis

We first provide analysis without adjustment of baseline demographics. For both the primary and secondary efficacy outcomes and principal and secondary safety outcomes, we use the Kaplan-Meier curve to estimate the survival functions of each group. If there is a presence of competing risks, cumulative incidence functions (CIFs) will be used to estimate the survival function⁷. The two-side log-rank test is used to measure if the apixaban 2.5 mg twice a day has a better survival chance than placebo (i.e., better chance of meeting the primary outcome). If there is a presence of competing risk, the log-rank based on cause-specific hazards⁸ will be used. The corresponding hazard ratio of treatment effect and its confidence interval will be reported.

While our analysis is based on randomization, we also provide confirmatory analyses with the adjustment of baseline demographics and clinical comorbidities since it may capture any potential variations to make the statistical analysis more powerful. We use Cox regression to assess both the primary and secondary efficacy outcomes, while with adjustment of baseline demographics and clinical comorbidities. No interaction effects will be added. If there are competing risks, a cause-specific hazard model⁷ will be used. The hazard ratio for being treatment with the apixaban 2.5 mg twice a day will be used to test the treatment effect. The hazard ratio of other baseline demographics will be reported as supplementary information.

If the trial has a good randomization, we expect that the hazard ratio of treatment in analysis with the adjustment of baseline demographics and its p-value implies the same conclusion as in analysis without adjustment of baseline demographics. However, if they are not consistent in

clinical interpretation, i.e., a) the interpretation directions are different; b) p-values indicate different conclusion of significance, we will use the hazard ratio of treatment in analysis with the adjustment of baseline demographics as the main results to report, and the results of unadjusted one is treated as supplementary materials.

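### SAP 6.4.1 lets an adjusted Cox model with open covariates and no named test displace the principal log-rank when the two conflict

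*Combined protocol and SAP*

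**What the plan says.** SAP 6.4.1, headed Principal Analysis, starts with an unadjusted comparison by two-sided log-rank test, on cause-specific hazards if there are competing risks. It continues: "we also provide confirmatory analyses with the adjustment of baseline demographics and clinical comorbidities". The reason given for adjusting is power. For the efficacy outcomes, the treatment hazard ratio from this Cox model "will be used to test the treatment effect", with no interaction terms.

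The section then states an expectation, beginning "If the trial has a good randomization, we expect that the hazard ratio of treatment", that the adjusted and unadjusted analyses will lead to the same conclusion. Two kinds of inconsistency are listed: a) the direction differs; b) "p-values indicate different conclusion of significance". Only a semicolon joins them. In that event "we will use the hazard ratio of treatment in analysis with the adjustment of baseline demographics as the main results to report", and the unadjusted result is kept as supplementary.

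Related text:
- **Covariates.** The model description names two classes, demographics and comorbidities. The replacement sentence names demographics only. SAP 6.3 gives examples ("such as age, sex, race, and comorbidities"), but for a descriptive table.
- **Deciding p-value.** In the SAP 6.2.1 table, the ITT row is the only one with a p-value for primary efficacy ("Number of events Proportion Cumulative incidence Hazard ratio 95% confidence interval P-value"). It names no model.
- **Protocol, Statistical Analysis Plan.** For baseline differences judged clinically relevant, "exploratory analyses that include the imbalanced factor as a categorized covariate will be performed". The protocol's only superiority rule uses a Mantel-Haenszel test with a Hochberg-adjusted p-value. The SAP does not refer to it.

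**The concern.** Which analysis heads the primary efficacy result depends on what the two analyses show, and the one that then prevails is the less fully specified. Covariates, coding, selection rule and test statistic (Wald, likelihood ratio or score) are all open. With few events these choices can move a p-value across 0.05. The claim at stake is superiority on recurrent VTE.

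The expectation attached to the rule also needs testing. If good randomization made the two analyses agree, disagreement would signal a randomization problem and could justify replacing the principal test. If disagreement is ordinary in well-randomized trials, it justifies nothing of the kind.

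**Working it through.** **1. The plan's own figures.** Inputs: 6% versus 1.5%, two-sided 0.05, 80% power, 300 per arm (protocol, Sample Size Calculation; SAP 6.1). With mean proportion 0.0375:

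n = [1.960 × √(2 × 0.0375 × 0.9625) + 0.842 × √(0.06 × 0.94 + 0.015 × 0.985)]² / 0.045² = 278.6, so 279 per arm, as the protocol states.

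Expected events: m = 300 × (0.06 + 0.015) = 22.5. The SAP 6.1 formula Φ(√m × |HR − 1|/(HR + 1) − 1.96) gives:
- HR 0.20: Φ(4.743 × 0.667 − 1.96) = Φ(1.20) = 88.5%
- HR 0.24: Φ(4.743 × 0.613 − 1.96) = Φ(0.95) = 82.8%

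Both agree with the SAP's aim of at least 80% at 600 patients. Neither calculation uses covariates.

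**2. What the rule does if a) and b) are alternatives.**

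| Log-rank | Adjusted Cox | Main result |
|---|---|---|
| significant | significant | significant |
| significant | not | not (adjusted) |
| not | significant | significant (adjusted) |
| not | not | not |

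The last column equals the second in every row. If a) and b) must both hold, the switch fired in 0 of the 72,000 trials of step 5 and in 0 of 12,000 trials of a separate simulation.

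**3. The test statistic alone can change the verdict.** Rare-event approximation, equal arms, events d0 and d1, no covariates:
- Score (log-rank): z = (d0 − d1)/√(d0 + d1)
- Wald: z = ln(d0/d1)/√(1/d0 + 1/d1)
- Likelihood ratio: χ² = 2[d0 ln(d0/e) + d1 ln(d1/e)], with e = (d0 + d1)/2

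| Events | Score p | Wald p | Likelihood ratio p |
|---|---|---|---|
| 12 vs 4 | 0.0455 | 0.057 | 0.041 |
| 9 vs 2 | 0.035 | 0.054 | 0.028 |

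**4. Disagreement with no covariates.** In 20,000 simulated randomized trials (600 patients, 6% vs 1.5%), an unadjusted Cox Wald test disagreed with the log-rank in 3.2%, always by losing significance. The likelihood ratio test disagreed in 0.25%. Under the null the figures were 0.8% and 0.1%.

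**5. Disagreement with adjustment.** 72,000 simulated trials: 600 patients 1:1, 12 months, exponential times, no loss. The covariate lists are assumed: 3 terms (7.5 events per term), the 6 variables named in SAP 6.3 (3.8), the 7 factors of protocol Table 3 (3.2), and all 13 (1.7). Prognostic strength ran from none to the full Table 3 risk ratios. Prevalences were also assumed (10–50%, with variants 5–35% and 20–55%). The Monte Carlo 95% margin at a 5% rate is 0.4 to 0.7 points. At the design effect:

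| Adjusted test | Disagree with log-rank | Log-rank overturned | Log-rank rescued | Less step 4 |
|---|---|---|---|---|
| Wald | 3.5–8.7% | 3.2–5.2% | 0.1–4.1% | 0.3–5.5 points |
| Likelihood ratio | 1.3–7.3% | 0.4–2.4% | 0.8–4.9% | 1–7 points |

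With non-prognostic covariates, disagreement was 3.5–5.1% (Wald) and 1.3–3.1% (likelihood ratio).

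**6. Error rate and power** (same simulation).

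| Test | Type I, fixed list | Type I, best of four lists | Power |
|---|---|---|---|
| Log-rank | 4.6–5.2% | – | 85.5–86.1% |
| Adjusted Wald | 3.8–5.6% | 4.9–7.6% | 81.9–85.5% |
| Adjusted likelihood ratio | 4.9–6.4% | 6.0–8.6% | 85.7–88.9% |

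The separate simulation (10 assumed binary covariates, four lists, two statistics, 3,000 trials per scenario) agrees in substance. A single fixed specification rejected in 4.5–6.0% under the null, and at least one of eight rejected in 6.7–8.1%. At the design effect the verdict depended on the specification in 7.5–12.9% of trials.

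**The case against.** Covariate adjustment is legitimate, and both results would be reported. If the truth table holds, the rule amounts to a fixed adjusted primary analysis, so the dependence on results is one of labelling. That is right as far as it goes, and it places the defect correctly: the adjusted model that would decide is left open.

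The consequence also needs two readings that the SAP does not state. One is that a) and b) are alternatives. This is the natural reading, because a changed significance verdict is already an inconsistency, and requiring both would leave the rule with nothing to do. The other is that the main reported result carries the superiority claim. This objection stands and limits how strongly the point can be put.

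Four stronger readings are tempting, and the documents do not support them:
- **Two chances at significance.** The rule does not accept whichever test is positive. With one list fixed in advance, type I error stays near 5%.
- **The verdict always follows the adjusted Cox model.** SAP 6.5 replaces the hazard ratio with restricted mean time lost ratios if proportional hazards fail.
- **All disagreement comes from adjustment.** Step 4 shows that most of the low-end Wald figure is choice of statistic.
- **The protocol makes every adjustment exploratory.** It says so only for observed imbalances judged clinically relevant.

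Nor does the rule reach major bleeding, since the adjusted Cox covers efficacy outcomes only, or interim stopping for efficacy, which SAP 6.9 bases on the unadjusted hazard ratio.

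**Conclusion.** The concern holds conditionally, and the text should be fixed. If a) and b) are alternatives, the main result carries the efficacy claim, and SAP 6.5 is not triggered, the primary efficacy verdict follows an adjusted model whose covariates, coding and test statistic are not fixed.

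The harm is room for choice after results are seen, plus a headline that depends on results. A free choice among the assumed specifications gives a type I error of about 5% to 9%. At the design effect, adjustment adds about 0.3–5.5 points of disagreement (Wald) or 1–7 points (likelihood ratio) beyond choice of statistic. The upper ends need covariates as prognostic as protocol Table 3. All ranges depend on assumed lists and prevalences and are not bounds.

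Every simulated trial was properly randomized, so disagreement is not evidence of poor randomization and gives no ground for replacing the principal test.

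**What to change.** In SAP 6.4.1, delete the replacement sentence. State that the unadjusted two-sided ITT log-rank (cause-specific) at 0.05 decides the final primary efficacy claim, whatever the adjusted model shows. Report the adjusted Cox as a sensitivity analysis, with a short covariate list, its coding and one named test statistic fixed before unblinding. The documents do not show whether unblinding has occurred. If it has, the list can no longer be prespecified: report both analyses and label the adjusted one supportive.

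Making one fully prespecified adjusted model primary before unblinding would also remove the defect. The log-rank is preferred because the SAP already treats it as principal and bases its power on an unadjusted comparison.

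The cost is wording, plus any power that adjustment would have gained: about 0 to 4 points under the assumed covariates. Against an adjusted Wald test there was no loss in these simulations (log-rank power was 0.4–3.7 points higher). Against an adjusted likelihood ratio test the loss was 0.3–3.1 points. Reconciling the protocol's Mantel-Haenszel and Hochberg rule with the SAP, and settling the status of the SAP 6.5 methods, are separate points.

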6.4.2 Subgroup Analysis

The study will conduct subgroup analyses based on certain predetermined factors such as whether the patient has PE versus non-PE, age (65 years or older versus younger), sex (male versus female), chronic kidney disease (defined as presence or absence of eGFR<60 mL/min/1.72m²), atherosclerotic cardiovascular disease (present versus absent), baseline low-dose aspirin use (present versus absent), the number of provoking risk factors (2 or more versus less than 2), provoking factor of travel, and baseline aspirin use. The survival analysis within each subgroup will be repeated using the main cohort and tested in confirmatory cohorts, as needed. The p-value of the additive interaction effect between treatment and subgroup will be reported.

In case the subgroup analysis of baseline aspirin use indicates a relevant modification effect (the p-value for the additive interaction effect <0.05), the study will repeat the primary analysis by reporting the treatment effect of apixaban vs placebo with the adjustments for a) the use of aspirin and b) the interaction term.

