In EINSTEIN CHOICE which randomized 60% of patients with provoked VTE, the control group received low-dose aspirin (which based on a meta-analysis in unprovoked VTE patients confers about a 33% relative risk reduction) had a recurrence rate of 3.6% (2,31). Accordingly, we would expect the 12-month VTE recurrence rate to be at least 33% higher in patients assigned to placebo in the proposed study and therefore approximately 5-6%. The recurrent VTE rate among placebo patients in the AMPLIFY-EXT trial of apixaban was quite a bit higher at 8.8% (7). By requiring that at least one additional persistent provoking VTE risk factor be present (persistent immobility, obesity, heart failure, chronic lung disease, chronic kidney disease, inflammatory disorder, or atherosclerotic cardiovascular disease), we will expect an “enriched” event rate in the population of the proposed study by at least 2-fold (all of these persistent provoking risk factors increase the risk of VTE by 2-4-fold; Table 3) (32). Many patients enrolled in the study will have multiple persistent provoking VTE risk factors (for example, heart failure, obesity, and atherosclerotic cardiovascular disease) and thereby have an even higher risk for recurrence. In an effort to be ultra-conservative, we kept the multiplier for this enriched study population to 2-fold (while in reality for many study patients it could be 4-fold or even higher). Accordingly, our estimate of a 12-month VTE recurrence rate of 6% is very conservative and still below the VTE recurrence rates reported in EINSTEIN VTE Continued Treatment and AMPLIFY EXT (neither of which included an enriched population).

Table 3. Relative risk of VTE by persistent provoking risk factor.

Persistent Provoking Risk Factor	Relative Risk
Persistent immobility	4-fold
Obesity (BMI ≥ 30)	2-3-fold
Heart failure	2-fold
Chronic lung disease	2-fold
Chronic kidney disease	2-fold
Inflammatory/autoimmune disorder	3-fold
Atherosclerotic cardiovascular disease	4-fold

Based on the data from EINSTEIN CHOICE, we conservatively estimate that low-intensity apixaban (2.5 mg twice daily) compared with placebo will provide a similar

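### SAP 6.4.2 pairs an additive interaction p-value with hazard ratios and, if aspirin is flagged, reports one treatment effect from an interaction model where it depends on the aspirin coding

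*Combined protocol and SAP*

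**What the plan says.** **Effect measure.** SAP 6.4.1 plans a log-rank test, cause-specific where there are competing risks, and then: "The corresponding hazard ratio of treatment effect and its confidence interval will be reported". Of the covariate-adjusted Cox model it says: "No interaction effects will be added".

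**Subgroups.** SAP 6.4.2 lists the subgroups, among them chronic kidney disease, atherosclerotic disease, number of provoking factors and baseline aspirin. It plans that "The survival analysis within each subgroup will be repeated using the main cohort" and adds: "The p-value of the additive interaction effect between treatment and subgroup will be reported". It names no additive-scale measure and no model for that p-value.

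**Aspirin.** The trigger for further analysis is "the p-value for the additive interaction effect <0.05". When it is met, the primary analysis is repeated by "reporting the treatment effect of apixaban vs placebo with the adjustments for a) the use of aspirin and b) the interaction term". No coding of aspirin and no rule for averaging over aspirin strata is given.

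**Protocol.** The Statistical Analysis Plan section of the protocol handles aspirin on a ratio scale. It calculates a risk ratio in each stratum and calls the effect modified if a stratum ratio is 10% or more away from the crude one.

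**The concern.** There are two separate problems.

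*Scale.* Additive interaction asks whether absolute differences vary between subgroups. If one hazard ratio holds throughout, absolute differences must vary wherever baseline risk varies. An additive p-value printed beside two subgroup hazard ratios therefore answers a different question from the one a reader will assume. Uniform relative efficacy could be read as effect modification.

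*Coefficient.* Once a treatment-by-aspirin product term is in the model, no single coefficient is the effect of apixaban versus placebo in the trial. Under 0/1 coding the apixaban term belongs to whichever aspirin group is the reference. The SAP would publish that number as a repeat of the primary analysis. It would do so only when the strata appear to differ, which is when one number describes the trial least well.

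**Working it through.** **Inputs from the documents.** Placebo risk 6%, a 75% reduction, 600 patients randomized 1:1 (SAP 6.1; protocol, Sample Size Calculation). Aspirin lowers recurrence by about 33%, a ratio of about 0.67 (protocol, Sample Size Calculation). **Assumed, because the documents give no figure:** the share on aspirin (35%; range 20-50%), the stratum hazard ratios in step 3, and the subgroup risk contrasts in step 2.

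**Background check.** The protocol's 279 per group at 6% vs 1.5% reproduces, with power 0.8005. No plan figure is disputed here. Expected events at 600 patients: 300 × 0.06 + 300 × 0.015 = 22.5.

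**Step 1: the two scales disagree under the plan's own inputs.** Take a ratio of 0.25 in both aspirin strata.
- No aspirin: 6.00% vs 1.50%, difference -4.50 points.
- Aspirin: 6 × 0.67 = 4.02% vs 4.02 × 0.25 = 1.005%, difference -3.015 points.
- Additive contrast: 4.50 - 3.015 = 1.485 points. Relative excess risk due to interaction: 0.25 × 0.67 - 0.25 - 0.67 + 1 = 0.2475.
- Ratio of the two treatment ratios: 0.25 / 0.25 = 1.

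Additive interaction is present and ratio-scale interaction is exactly nil.

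**Step 2: how often the additive p-value is below 0.05 with a uniform hazard ratio of 0.25.** With 35% users there are 105 users and 195 non-users per arm. Placebo risks of 4.5% and 6.8% average 0.35 × 4.5 + 0.65 × 6.8 = 5.995%, and their ratio is 0.66. Apixaban risk is 1 - (1 - p)^0.25, which gives 1.14% and 1.75%. A Wald test of the difference between the two risk differences, over 200,000 simulated trials, rejects in about 10%.

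With two equal subgroups (150 per arm in each):

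| Placebo risks | Rejection rate |
|---|---|
| Equal, 6% and 6% | 4.9% |
| 4% and 8% | 16% |
| 3% and 9% | 30% |
| 2.4% and 9.6% | 41% |

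In every row but the first the additive null is false, so these rates are power on the additive scale.

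**Step 3: what the interaction model reports.** Write log hazard = baseline + b1·T + b2·A + b3·T·A, with T = apixaban and A = aspirin (0/1). The apixaban hazard ratio is exp(b1) when A = 0 and exp(b1 + b3) when A = 1. Cox models were fitted to one large simulated data set (400,000 patients, 35% on aspirin, aspirin ratio 0.67, assumed true hazard ratios 0.25 without and 0.75 with aspirin):

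| Model | Apixaban term, as a hazard ratio |
|---|---|
| Interaction, reference = no aspirin | 0.24 |
| Interaction, reference = aspirin | 0.76 |
| Interaction, aspirin mean-centred | 0.36 |
| No interaction, aspirin-adjusted | 0.38 |
| Unadjusted | 0.38 |

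The first three rows are the same fitted model. Only the coding differs.

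**Step 4: precision.** Take hazard ratio 0.25 in both strata, 35% users, and step 1 risks. Expected events are 11.7 and 2.925 (non-users, placebo and apixaban) and 4.22 and 1.06 (users).
- SE of the no-aspirin term: √(1/11.7 + 1/2.925) = 0.654.
- SE of the interaction: √(1/11.7 + 1/2.925 + 1/4.22 + 1/1.06) = 1.27.
- Ratio of hazard ratios detectable with 80% power: exp(2.8 × 1.27) = 35.

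Over 20-50% users, the detectable ratio runs from 78 down to 27, and the power of the no-aspirin term alone runs from 65% down to 46%. A one-stratum figure would be far too imprecise to stand as a repeat of the primary result.

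**The case against.** The strongest reply is that *additive* may mean no more than a product term added to the Cox model. The SAP goes on to speak of an interaction term, and Cox is the regression model named in 6.4.1. On that reading the test is already of the ratio of hazard ratios and step 2 does not apply. This stands as a possibility. But the word has an established other meaning and nothing in 6.4.2 settles which is intended, so an analyst could run either test. The coefficient problem is the same on both readings.

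On the coefficient, three replies have some force. Centred coding gives an average over strata, but no coding is stated, so the reported quantity stays undefined. Items a) and b) could be two separate models; a) would then be a sound aspirin-adjusted estimate and the problem confined to b). And the within-subgroup analyses already yield both aspirin-stratum hazard ratios. That softens the harm, but the clause still promises a single treatment effect.

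A reader might infer that the clause displaces the primary result. The documents do not support that. SAP 6.4.2 speaks of repeating the analysis. Where the SAP means one result to take over as the main one, as for the covariate-adjusted model in 6.4.1, it says so. The table in 6.2.1 keeps the ITT hazard ratio, confidence interval and p-value for primary efficacy. Nor does the ban on interaction effects in 6.4.1 contradict 6.4.2, since it governs the covariate-adjusted confirmatory model.

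**Conclusion.** The point holds as a moderate error in a conditional secondary analysis. Read literally, the interaction p-value does not match the hazard ratios beside it. The aspirin clause yields a treatment effect that depends on an unstated coding choice (0.24 or 0.76 in the worked case, against 0.38 overall). Both follow from the structure of the models. Their size rests on the assumed aspirin share, stratum hazard ratios and risk contrasts.

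Two stronger readings are tempting and should not be drawn. The first is that the rates in step 2 are inflated false-positive rates, or that uniform efficacy *would* be reported as effect modification. Additive interaction is real in those scenarios, and even so 59% to 84% of trials in the 2- to 4-fold cases, and about 90% for aspirin, show no p-value below 0.05. *Could* is as far as it goes. The second is that the documents establish 3- or 4-fold contrasts between these subgroups. The protocol does say that "all of these persistent provoking risk factors increase the risk of VTE by 2-4-fold", but its Table 3 gives relative risk of VTE by factor. It does not give recurrence risk within a trial where every patient must carry at least one such factor, so most comparison groups carry another.

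**What to change.** In SAP 6.4.2:

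1. Define each interaction p-value as the test of the treatment-by-subgroup product term in the Cox model (cause-specific where there are competing risks), and drop the word *additive*.
2. When the aspirin interaction is flagged, report the apixaban hazard ratio and confidence interval in each aspirin stratum, in place of a single treatment effect from the interaction model.
3. State that the ITT hazard ratio remains the overall result. If an aspirin-adjusted overall hazard ratio is wanted, take it from a model without the interaction term.
4. Show absolute differences by subgroup descriptively, if wanted.

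Two tidying steps belong in the same edit: reconcile the SAP's p-value trigger with the protocol's 10% rule, and remove the second listing of aspirin among the subgroups. Given step 4 of the working, add a sentence that a non-significant interaction is not evidence of a uniform effect.

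The cost is a few sentences and slightly simpler programming. No change is needed to data collection, sample size or the primary analysis.
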